**Table 1: Schedule of Events - Screening through Week 16 Visit**

Study Week	Screening Period	Pre-Randomization Period	Treatment Period				
		Pre-Randomization Phone Call	(Baseline)	4	8	12	16
Study Day (visit window)	Up to 30 days	7 to 10 days	1	29 (±7)	57 (±7)	85 (±7)	113 (±7)
Screening/Baseline:							
Informed Consent	X						
Inclusion/Exclusion 	X	X	X				
Genomics sub-study informed consent 	X						
Medical History	X						
Medication history	X						
Demographics	X						
Height	X						
Electrocardiogram	X						
Bilateral radiograph (knee, hip, shoulder) 	X 						
WOMAC Pain Subscale	X 		X				
MRI 	X						
Randomization			X				
Treatment:							
Discontinue non-study pain meds		X					
SC Study Drug Injection 			X	X	X	X	X
Dispense paracetamol/acetaminophen			X	X	X	X	X

Study Week	Screening Period	Pre-Randomization Period	Treatment Period				
		Pre-Randomization Phone Call	(Baseline)	4	8	12	16
		7 to 10 days	1	29 (±7)	57 (±7)	85 (±7)	113 (±7)
Paracetamol/acetaminophen accountability				X	X	X	X
Dispense NSAID medication							X
Recording of rescue treatment use in diary 			X	X	X	X	X
Concomitant medications	X	X	X	X	X	X	X
Safety:							
Weight	X						X
Vital Signs 	X		X	X	X	X	X
Physical Examination	X						X
Injection site evaluation			X	X	X	X	X
Orthostatic blood pressure 	X		X	X	X	X	X
Joint Pain Questionnaire	X		X	X	X	X	X
Survey of autonomic symptoms	X		X	X	X	X	X
Neurologic examination	Full		Brief	Brief	Brief	Brief	Full
Adverse Events	X	X	X	X	X	X	X
Event-triggered imaging 				X	X	X	X
Pre-op questionnaire (JR) 							
Laboratory Testing:							
Hematology	X						X
Blood Chemistry	X			X	X		X
Erythrocyte sedimentation rate	X						

Study Week	Screening Period	Pre-Randomization Period	Treatment Period				
		Pre-Randomization Phone Call	(Baseline)	4	8	12	16
Study Day (visit window)	Up to 30 days	7 to 10 days	1	29 (±7)	57 (±7)	85 (±7)	113 (±7)
HbA1c	X						
FSH and estradiol 	X						
Pregnancy test (WOCBP)	Serum 		Urine 	Urine 	Urine 	Urine 	Urine 
Urinalysis and Urine Creatinine and Phosphorous	X			X	X		X
PK/Drug Concentration and ADA Samples:							
PK/Drug concentration sample 							X
ADA sample 			X				X
Genomics sub-study sample 			X				

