Neurologic examination	Full	Full	Full	Full	Full	Full	Full
Bilateral radiograph (knee, hip, shoulder) 		X				X	X
Adverse Events	X	X	X	X	X	X	X

Study Week	Week 20 Clinic Visit	Week 24 Clinic Visit	Week 28 Clinic Visit	Week 32 Clinic Visit	Clinic Visits Between Week 36 and End of Treatment	Week 52 or End of Treatment Visit 	Early Termination/JR Pre-operative Visit
Visit Window	Q4W (±7 days)	(±7 days)	(±7 days)	(±7 days)	(±7 days)	(±7 days)	
Event-triggered imaging 	X	X	X	X	X	X	X
Pre-op questionnaire (JR) 							X 
Laboratory Testing:							
Hematology				X		X	X
Blood Chemistry				X		X	X
Pregnancy test (WOCBP)	Urine 	Urine 	Urine 	Urine 	Urine 	Urine 	Urine 
Urinalysis and Urine Creatinine and Phosphorus				X		X	X
PK/Drug Concentration and ADA Samples:							
PK/Drug conc. sample 				X		X	X
ADA sample 				X		X	X
Research serum/plasma sample 						X	X

ADA: Anti-drug antibody; FSH: Follicle stimulating hormone; JR: Joint replacement; MRI: Magnetic resonance imaging; NSAID: Non-steroidal anti-inflammatory drug; PK: Pharmacokinetic; WOCBP: Women of child-bearing potential; WOMAC: Western Ontario and McMaster Universities Osteoarthritis Index

1. If treatment is stopped for patients (for example, due to conditions in Section 3.1 or Section 5.3.2.1 being met or for other reasons per the patient or investigator), patients should complete the end of treatment/week 52 assessments at their next scheduled visit. All subsequent visits should be conducted according to the schedule of events and all procedures should be completed, except for study medication administration. Imaging does not need to be repeated at a routine visit if all radiographs were conducted within 30 days and submitted for central reading.
2. Study drug administration will be the last procedure at each dosing visit, and will be done after all laboratory samples have been collected and all study assessments and procedures are performed.
3. Patients will record their daily use of paracetamol/acetaminophen and NSAIDs from the week 16 visit through week 52.
4. If the pulse is less than 45 bpm at any visit after the randomization visit, an ECG with rhythm strip will be obtained and sent to the central reader to confirm the heart rate and rhythm.

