Urinary drug test	X								X	
PK/Drug Concentration:										
PK/Drug concentration sample			X			X	X		X	X

JR: Joint replacement; NRS: Numerical Rating Scale; OA: Osteoarthritis; PK: Pharmacokinetic; WOMAC: Western Ontario and McMaster Universities Osteoarthritis Index

1. Walking index joint pain NRS score will be recorded by the site at the pre-randomization visit, and by the patient each day using their diary, starting during the pre-randomization period through week 16.
2. At the screening visit, the WOMAC pain sub-scale will be evaluated for both knees and both hip joints.
3. WOMAC full survey for index joint only.

**Table 4: Schedule of Events - Follow-up Period (24 Weeks after Last Treatment) and End of Study Phone Contact (52 Weeks after Last Treatment)**

	Phone call 8 weeks post last dose	Clinic Visit 12 weeks post last dose	End of Follow up Clinic Visit 24 weeks post last dose	End of Study Phone call 52 weeks post last dose	Early Termination/JR Pre-Operative Visit
Study Week	Up to week 56 (±7 days)	Up to week 60 (±7 days)	Up to week 72 (±7 days)	Week 100 (±7 days)	During the Follow-up Period
Treatment:					
Concomitant medications	X	X	X		X
Safety:					
Adverse Events	X	X	X		X
Weight		X	X		X
Vital signs 		X	X		X
Physical examination		X	X		X
Electrocardiogram		X	X		X
Orthostatic blood pressure		X	X		X
Joint pain questionnaire		X	X		X
Survey of autonomic symptoms		X	X		X
Neurologic examination		Full	Full		Full
Bilateral radiograph (knee, hip, shoulder) 		X	X		X
Event-triggered imaging 		X	X		X
Pre-op questionnaire 					X
End of study phone contact 				X	
MRI of affected joint(s) for AA patients only 				X	
Laboratory assessments					
Hematology			X		X
Blood Chemistry			X		X
Pregnancy test (WOCBP)			Urine 		Urine 
Urinalysis and Urine Creatinine and Phosphorous			X		X

	Phone call 8 weeks post last dose	Clinic Visit 12 weeks post last dose	End of Follow up Clinic Visit 24 weeks post last dose	End of Study Phone call 52 weeks post last dose	Early Termination/JR Pre-Operative Visit
Study Week	Up to week 56 (±7 days)	Up to week 60 (±7 days)	Up to week 72 (±7 days)	Week 100 (±7 days)	During the Follow-up Period
PK/Drug Concentration and ADA Samples:					
PK/Drug concentration sample 		X	X		X
ADA sample 			X		X
Research serum/plasma sample 			X		X

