4.5. Safety Variables

Patient safety will be assessed through the collection of reported adverse events (AEs), clinical laboratory data, vital signs, ECG, Survey of Autonomic Symptoms Questionnaire, neurological exams and physical exams. Unless otherwise noted, the baseline value is defined as the last available value before the first dose of study drug.

Adverse events (AE) and Serious Adverse Events (SAE) will be collected from the time of informed consent signature and then at each visit until the End of Follow-up Clinic Visit. All AEs are to be coded to a “Preferred Term (PT)” and associated primary “System Organ Class SOC” according to the MedDRA[®] (the latest current available version).

An Adverse Event is any untoward medical occurrence in a patient or clinical investigation patient administered a pharmaceutical product and which does not necessarily have to have a causal relationship with this treatment.

A Serious Adverse Event is an adverse event (AE) that is classified as serious according to the criteria specified in the protocol.

Laboratory results, vital signs, or ECG abnormalities are to be recorded as AEs if they are medically relevant: symptomatic, requiring corrective therapy, leading to treatment discontinuation and/or fulfilling a seriousness criterion.

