4.5.9. Physical and Neurological Examination Variables

Patients will have a physical examination including an examination of the knees, hips, and shoulders performed according to the Schedule of Events in [Appendix 11.1](#). The result for each body system is an outcome of normal or abnormal. Neurological evaluations of specific domains as listed in the protocol will be described as normal or abnormal.

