5.1.8.9. Neurological Exam

The number and percentage of patients with new-onset abnormal neurological examinations will be summarized by Neurological evaluations by visit based on the LTS-SAF.

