6.1. Definition of Baseline for Variables

Unless otherwise specified, the baseline assessment for all measurements will be the latest available valid measurement prior to randomization.

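### The SAP's default baseline lets the day 1 Brief neurologic examination override the Full screening one, so abnormalities already found at screening can be counted as new-onset

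*Protocol*

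**What the plan says.** The examination row of Protocol Table 1 reads "Neurologic examination Full Brief Brief Brief Brief Full". Set against the column heads, that is Full at screening, none at the pre-randomization phone call, Brief on day 1 and at weeks 4, 8 and 12, and Full at week 16. Tables 2 and 4 show Full wherever the examination is scheduled.

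Protocol 6.3.4.7 gives one list of domains (motor, sensory, cranial nerves, reflexes, coordination and balance, plus signs of carpal tunnel syndrome). It leaves the content of the full and brief versions to the study reference manual.

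On the analysis side:

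- SAP 4.5.9: "Neurological evaluations of specific domains as listed in the protocol will be described as normal or abnormal".
- SAP 5.1.8.9: "The number and percentage of patients with new-onset abnormal neurological examinations will be summarized by Neurological evaluations by visit". New-onset is not defined.
- SAP 4.5: "Unless otherwise noted, the baseline value is defined as the last available value before the first dose of study drug".
- SAP 6.1, also a default: "the baseline assessment for all measurements will be the latest available valid measurement prior to randomization".

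Neither baseline rule makes an exception for the neurologic examination.

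**The concern.** The Full screening examination is the only pre-dose examination of the same type as those from week 16 onward. The default baseline rule can replace it with a shorter one. A patient whose sensory domain, say, was abnormal at screening but was recorded as normal on the day 1 Brief examination would then be normal at baseline. The first Full examination, at week 16, could turn that patient into a new-onset case.

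The summary bears on a risk the protocol takes seriously. Protocol 7.6.1.3 calls altered peripheral sensation an important identified risk, and Protocol 1.1 reports vibration-sense abnormalities more often on fasinumab than on placebo. If pre-existing findings enter the counts in every arm, the new-onset figures are too high, the ratio between arms is pulled toward 1, and part of any rise at week 16 reflects the change of examination type.

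**Working it through.** The plan states no rate or power for this summary, so there is no figure to reproduce. The first part of the check is logical.

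1. **Which examination is last before first dose?** Table 1, footnote 5, makes study drug the last procedure at each dosing visit. The day 1 Brief examination therefore precedes the first dose and is the last one under SAP 4.5. Under SAP 6.1 the answer depends on whether the examination comes before or after randomization on day 1, an order the documents do not state.

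2. **What happens domain by domain?**

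| Situation | Baseline under SAP 4.5 | Screening abnormality counted as new-onset? |
|---|---|---|
| Baseline per domain; Brief omits the domain | Full screening result | No |
| Baseline per domain; Brief tests the domain as fully as Full | Day 1 result, like for like | Not through the change of examination type |
| Baseline per domain; Brief tests the domain less fully | Day 1 Brief result | Possible |
| Baseline per visit | Day 1 Brief examination | Possible |

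The documents do not say which row applies.

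3. **How does the SAP treat the same problem elsewhere?** SAP 5.1.8.3 requires a treatment-emergent laboratory PCSV to have been normal at both screening and baseline. The neurologic summary has no such condition.

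4. **What would the error do?** Let q be the share of patients abnormal on Full at screening but normal on Brief at day 1, and r the true new-onset proportion in an arm. Suppose q is equal across arms, as randomization would make it on average, and every such abnormality is found again at the Full visit. Then:

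- reported proportion = q + (1 − q)r
- reported difference = (1 − q)(r₁ − r₀)

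All values of q and r here are assumptions. With r₁ = 5.0% and r₀ = 2.5% (true ratio 2.0, true difference 2.50 points):

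| q | Reported proportions | Ratio | Difference (points) |
|---|---|---|---|
| 2% | 6.90% vs 4.45% | 1.55 | 2.45 |
| 5% | 9.75% vs 7.38% | 1.32 | 2.38 |
| 10% | 14.50% vs 12.25% | 1.18 | 2.25 |

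Other assumed rates give the same pattern. With 5% vs 3% (true ratio 1.67, difference 2.00 points), q from 2% to 10% gives ratios from 1.40 to 1.14 and differences from 1.96 to 1.80 points. With 10% vs 6% (true ratio 1.67, difference 4.00 points), the ratios run from 1.50 to 1.23 and the differences from 3.92 to 3.60.

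The inflation in an arm is q(1 − r), close to q when r is small. For q = 2% and r = 2.5% it is 0.02 × 0.975 = 1.95 points.

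**The case against.** A reader might infer that the screening result is always displaced and that the plan will therefore report old findings as new. The documents do not go that far. The rule refers to the last available value, and SAP 4.5.9 records results by domain. A domain left out of the Brief examination keeps its Full screening result. Whether any shared domain is tested less fully on day 1 depends on the study reference manual. New-onset is undefined in SAP 5.1.8.9, so a programmer could read it sensibly.

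The affected share may also be small. Protocol 4.2.3 excludes neuropathic disorders, multiple sclerosis, recent carpal tunnel signs, and autonomic, diabetic or other peripheral neuropathy. The same clinician is to examine whenever possible. To be affected, a patient must be abnormal at screening, normal at most about 40 days later (30 days of screening plus 7 to 10 days of pre-randomization), and then abnormal again. No document supports q of 2% to 10%.

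Finally, SAP 5.1.8.9 is a descriptive count and percentage. The rate-ratio model in SAP 5.1.7.1 is for the primary safety endpoints, and the list in SAP 4.5.1 does not name the neurologic examination. Peripheral sensory AESIs are captured separately, and Protocol 6.3.4.7 sends non-exclusionary baseline findings to medical history.

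All of this limits the size and reach of the problem. It does not close the gap. Where the Brief examination does score a domain, the stated default makes that score the baseline, and nothing in the SAP brings the screening result back.

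**Conclusion.** The point holds as a conditional weakness in one descriptive safety summary. It takes effect if the Brief examination tests a shared domain less fully, or if baseline is derived per visit. In either case, abnormalities already found at the Full screening examination can enter the SAP 5.1.8.9 counts as new-onset.

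The effect would be similar inflation in all arms and a diluted ratio between arms. The absolute difference would shrink only by the factor (1 − q). This rests on q being balanced by randomization and on findings being re-detected equally across arms.

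The ratios and differences in the working show direction and shape only. The actual size cannot be derived from the documents. A reader might infer from those ratios that a real signal would be hidden, or that a false difference between arms would appear. The documents support neither reading: the inputs are assumed, the plan specifies no ratio for this summary, and the mechanism adds about the same number of percentage points to each arm.

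**What to change.** In SAP 5.1.8.9 and 4.5.9, define new-onset for each domain as an abnormal result after first dose with no abnormal result at either the Full screening or the day 1 Brief examination. This matches the principle of the laboratory PCSV rule in SAP 5.1.8.3. It works whatever the Brief examination covers, because a domain not scored on day 1 is judged on screening alone. It also makes the different baseline anchors in SAP 4.5 and 6.1 irrelevant to this summary.

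Using the screening examination alone as the comparator at Full visits would not do. A patient normal at screening but abnormal on day 1 before dosing would then be counted as new-onset.

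The cost is a sentence or two of SAP text and one derivation, since both pre-dose examinations are already collected. The definition will not necessarily remove the whole step at week 16. Abnormalities that arise after dosing and are missed by the Brief examinations at weeks 4 to 12 may still first appear at the week 16 Full examination, and a footnote to the table should say so.

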**Table 5: Schedule of Events - Follow-up for Patients Who Undergo Joint Replacement Surgery**

Follow-up Study Day (Visit Window)	Follow-up Period 	
	Post-Operative	Long-Term
	Follow-up Visit 1 4 weeks after the date of the joint replacement surgery	Follow-up Visit 2 20 weeks after the date of the joint replacement surgery
	F/U Day 29 (±5)	F/U Day 140 (±7)
Treatment:		
Concomitant medications	X	X
Safety:		
Adverse events	X	X
Vital signs	X	X
Orthostatic blood pressure 	X	X
Physical examination with joint exam	X 	X
Medical history related to the joint replacement	X	X
Joint pain questionnaire	X	X
Post-operative assessment questionnaire 	X	X
Bilateral radiograph (knee, hip, shoulder) 	X 	X
Event-triggered imaging 	X	X

F/U: Follow-up

- All available information for patients who undergo JR surgery must be collected, including placement of the prosthesis, healing of the surgical wound, and the results of the histopathologic examination.
- Knee Society Score questionnaire for knee replacements or Harris Hip Score questionnaire for hip replacements.
- Imaging (x-ray and/or MRI) will be performed on any joint following a report of clinically significant worsening or exacerbation of pain in that joint.
- If it is not possible to obtain orthostatic blood pressure following JR then blood pressure and pulse should be recorded.
- In the event of more than 1 JR, imaging assessments should be repeated if it has been >60 days since the joints were last imaged. If it has been ≤60 days since imaging assessments were completed, imaging assessments may be completed at the discretion of the investigator. An MRI may be requested by the imaging vendor after review of the x-rays.
- Imaging will be done at week 4 if not done pre-operatively.

## 6.2. Study Visit Descriptions

### 6.2.1. Screening Period (Up to 30 days)

Informed consent must be obtained prior to any screening procedures. After informed consent has been obtained, patients may be screened for eligibility. The screening window is 30 days from the time the informed consent has been signed. If the patient has not met screening eligibility criteria by the end of the 30-day screening window, the patient will be identified as a screen failure. Patients who screen fail may rescreen per Section 6.2.2. Laboratory assessments used to determine eligibility may be repeated during the screening period. The procedures outlined in the schedule of events should be completed during the screening period (Table 1).

When applicable, all pain assessments at the screening visits and subsequent visits should be completed prior to the physical examination. The patient reported outcomes assessments should be completed prior to all other efficacy assessments.

After the patient has otherwise met study eligibility criteria assessed during the screening period, an MRI will be performed prior to the pre-randomization phone call/visit for the index and contralateral joint and well as any knee or hip joint with a K-L score  $\geq 3$ . Confirmation from the central reader that there are no exclusionary findings on MRI must be received before a patient can be randomized.

### 6.2.2. Rescreening

Patients who do not meet eligibility criteria may rescreen once and only after approval of the sponsor or designee. Rescreening may occur if it is believed by the investigator that the reason for screen failure was due to a condition that would resolve or could be treated, or a laboratory value that minimally exceeded the cut-off value and is not clinically relevant. Patients cannot rescreen if they have screen failed due to not meeting the WOMAC criteria or have orthostatic hypotension. Rescreening can be completed for patients who fail to meet the screening visit window requirements or who are unable to complete all imaging assessments within the specified screening period. Patients who screen failed under amendment 3, 4 or 5 may rescreen under amendment 6 if they have not previously rescreened.

Only the assessments that did not meet eligibility criteria during the first screening are required to be repeated during the rescreen, if done within the screening period or pre-randomization period. Patients who are rescreened after the screening and pre-randomization windows end, must re-consent for study participation and repeat all screening procedures with the exception of imaging assessments. Any imaging assessments need to be repeated only if they were taken more than 60 days from when previous screening X-rays and MRI assessments were completed.

### 6.2.3. Pre-Randomization Period (7 to 10 days)

Following the screening period, patients will complete a 7 to 10 day pre-randomization period. Patients who are not participating in the sub-study will complete the pre-randomization visit as a telephone contact. Sub-study patients will return to the clinic for a pre-randomization visit 7 to 10 days before the randomization visit. During the pre-randomization period, all patients will be instructed to stop using their standard-of-care pain medications and to use only paracetamol/acetaminophen as rescue treatment. In addition, sub-study patients should

discontinue use of paracetamol/acetaminophen 24 hours prior to the start of the randomization visit (baseline).

#### **6.2.4. Baseline/Randomization Visit (Day 1)**

If a patient has met all screening eligibility criteria, study sites will complete the procedures as detailed in the schedule of events for the baseline visit. The patient-reported outcomes assessments at this and subsequent visits should be completed prior to all other assessments. During treatment period 1 (screening to week 16), patients will be observed in the clinic for approximately 1 hour for evidence of a hypersensitivity reaction following study drug administration. Paracetamol/acetaminophen will be provided to patients to be used as rescue treatment, taken as needed, according to local standards-of-care, to a maximum total dose of 2500 mg in Europe and 2600 mg in countries outside of Europe per day, starting on day 1. All use of NSAIDs, including oral or topical formulations, is prohibited. Patients will record their daily use of rescue treatment using a diary starting from the randomization visit through the end of treatment. All laboratory samples at this and subsequent visits must be collected and all study procedures must be performed before study drug is administered. At dosing study visits, urine pregnancy testing will be done and read before the study drug is administered. In the event of a positive urine pregnancy test result, the patient should have a serum pregnancy test with a negative result in order to continue study participation. If the serum pregnancy test is positive, the patient should be withdrawn from study drug and should be asked to return to the clinic for all remaining study visits per the visit schedule (see Section 5.3.2).

The date of the first dose of study drug is designated on day 1. All subsequent visits should be scheduled based on this date.

